5.3 Immediately Reportable Events

The investigator must immediately report after either the investigator or site personnel become aware of any SAE, potential serious hepatotoxicity, or confirmed pregnancy, by telephone, fax, or e-mail to the sponsor using the contact information on the cover page of this protocol. An IRE form must be completed and sent by e-mail, fax, or overnight courier to the sponsor. (Please note that the IRE form is NOT the AE eSource).

Subjects experiencing SAEs should be followed clinically until their health has returned to Phase A baseline status, or until all parameters have returned to normal or have otherwise been explained. It is expected that the investigator will provide or arrange appropriate supportive care for the subject and will provide prompt updates on the subject’s status to the sponsor.

5.4 Potential Serious Hepatotoxicity

For a subject who experiences an elevation in AST or ALT that is ≥ 3 times the ULN, a total bilirubin level should also be evaluated. If the total bilirubin is ≥ 2 times the ULN, complete an IRE form with all values listed and also report as an AE on the eSource.

Protocol 331-201-00079

5.5 Pregnancy

Women of child-bearing potential (WOCBP) are defined as female subjects for whom menstruation has started and who are not documented as sterile (ie, have had a bilateral oophorectomy and/or hysterectomy or who have been postmenopausal for at least 12 months).

For WOCBP and for men who are sexually active, there must be a documented agreement that the subject and/or their partner will take effective measures (ie, double-barrier method) to prevent pregnancy during the course of the trial and for 30 days after the last dose of IMP. Unless the subject is sterile (ie, women who have had a bilateral oophorectomy and/or hysterectomy or who have been postmenopausal for at least 12 consecutive months; or men who have had a bilateral orchidectomy) or remains abstinent, 2 of the following precautions must be used: vasectomy, tubal ligation, vaginal diaphragm, intrauterine device, birth control pills, birth control depot injection, birth control implant, condom with spermicide, or sponge with spermicide. Any single method of birth control, including vasectomy and tubal ligation, may fail, leading to pregnancy. The contraceptive method will be documented at each trial visit.

Before enrolling WOCBP in this clinical trial, investigators must review the below guidelines about trial participation with all WOCBP. The topics should generally include:

- General information
- ICF
- Pregnancy prevention information
- Drug interactions with hormonal contraceptives
- Contraceptives in current use
- Guidelines for the follow-up of a reported pregnancy

Before trial enrollment, WOCBP must be advised of the importance of avoiding pregnancy during trial participation and the potential risk factors for an unintentional pregnancy. The subject must sign an eICF stating that the above-mentioned risk factors and the consequences were discussed with her.

A urine and/or serum pregnancy test for human chorionic gonadotropin (hCG) will be performed at screening on all WOCBP. If a urine test is performed and is positive, the investigator will follow up with a confirmatory serum test.

During the trial, all WOCBP should be instructed to contact the investigator immediately if they suspect they might be pregnant (eg, missed or late menstrual cycle).

Protocol 331-201-00079

If a subject is suspected to be pregnant before she receives IMP, the IMP administration must be withheld until the results of serum pregnancy tests are available. If the pregnancy is confirmed, the subject must not receive the IMP and must not be enrolled in the trial. If pregnancy is suspected while the subject is taking IMP, the IMP must be withheld immediately (if reasonable, taking into consideration any potential withdrawal risks) until the result of the pregnancy test is known. If pregnancy is confirmed, the IMP will be permanently discontinued in an appropriate manner (eg, dose tapering if necessary for subject safety) and the subject will be withdrawn from the trial. Exceptions to trial discontinuation may be considered for life-threatening conditions only after consultations with the Clinical Safety and Pharmacovigilance department (see the cover page of this protocol for contact information).

The investigator must immediately notify the sponsor of any pregnancy associated with IMP exposure during the trial and for 30 days after the last dose of IMP, and record the event on the IRE form and forward it to the sponsor. The sponsor will forward Pregnancy Surveillance Form(s) for monitoring the outcome of the pregnancy.

Protocol-required procedures for trial discontinuation and follow-up must be performed on the subject unless contraindicated by pregnancy (eg, x-ray studies). Other appropriate pregnancy follow-up procedures should be considered, if indicated. In addition, the investigator must report to the sponsor, on appropriate Pregnancy Surveillance Form(s), follow-up information regarding the course of the pregnancy, including perinatal and neonatal outcome. Infants will be followed for a minimum of 6 months from the date of birth.

5.6 Procedure for Breaking the Blind

The investigator is encouraged to contact the sponsor/CRO medical advisor to discuss their rationale for unblinding. However, to prevent delays to the investigator or medical personnel responding to a potentially emergent situation, unblinding of IMP will not be dependent upon the investigator receiving approval from the sponsor/CRO medical advisor (ie, the investigator will be able to obtain the code break information independent of the sponsor/CRO medical advisor). The investigator must contact the sponsor/CRO medical advisor by telephone or e-mail with an explanation of the need for opening the treatment assignment code within 24 hours of opening the code. If the blind is broken, the Clinical Safety and Pharmacovigilance department must be notified immediately (see the cover page of this protocol for contact information). Documentation of breaking the blind should be recorded in the subject's medical record with the date and time the blind was broken and the names of the personnel involved. Once the blind is broken for a subject, that subject may not reinitiate treatment with the IMP.

Protocol 331-201-00079

5.7 Follow-up of Adverse Events

5.7.1 Follow-up of Nonserious Adverse Events

Nonserious AEs that are identified at any time during the trial must be recorded on the AE eSource with the current status (ongoing or resolved or recovered) noted. All nonserious events (that are not IREs) that are ongoing at the last scheduled contact will be recorded as ongoing on the eSource. For any AE having been identified throughout the trial, during analysis, additional relevant medical history information may be requested by the sponsor to further ascertain causality (including, but not limited to, information such as risk-related behavior, family history and occupation).

5.7.2 Follow-up of Serious Adverse Events and Immediately Reportable Events

This trial requires that subjects be actively monitored for SAEs and IREs up to 21 (± 2) days after the last dose of IMP is administered.

Serious AEs and nonserious IREs that are **identified or ongoing at the last scheduled contact** must be recorded as such on the AE eSource page. If updated information (eg, resolved status) on SAE or IRE status becomes available after a subject's last scheduled contact (up to last in-clinic visit for the entire trial), this must be reported to the sponsor and recorded on the AE eSource page, according to the appropriate reporting procedures. The investigator will follow SAEs until the events are resolved, stabilized, or the subject is lost to follow-up or has died. Resolution means that the subject has returned to the Phase A baseline state of health and stabilized means that the investigator does not expect any further improvement or worsening of the subject's condition. The investigator will continue to report any significant follow-up information to the sponsor up to the point the event has resolved or stabilized, or the subject is lost to follow-up or has died.

5.7.3 Follow-up and Reporting of Serious Adverse Events and Immediately Reportable Events Occurring after Last Scheduled Contact

Any new SAEs or IREs reported to the investigator which occur **after the last scheduled contact** and are determined by the investigator to be reasonably associated with the use of the IMP, should be reported to Syneos Health. This may include SAEs or IREs that are captured on follow-up telephone contact or at any other time point after the defined trial period. The investigator should follow SAEs and IREs identified after the defined trial period and continue to report any significant follow-up information to the Syneos Health until the events are resolved or stabilized, or the subject is lost to follow-up or has died.

Protocol 331-201-00079

6 Pharmacokinetic/Pharmacogenomic Analysis

Collected blood samples in the Stabilization Phase (Phase B) during the Week 16 and Week 20 visits and in Double Blind Randomized Withdrawal Phase (Phase C) during the Week 37 and Week 46/ET visit will be analyzed for plasma concentrations of brexpiprazole. The samples will be collected at the same time of collection of clinical laboratory samples and the time of the last 3 doses prior to the PK sampling will also be collected at the time of PK sample collection.

A sample to assess the CYP2D6 metabolizing status and other enzymes will be collected at the Week 20/Randomization visit. [REDACTED]

7 Statistical Analysis

Complete details of the planned statistical analysis will be presented in the statistical analysis plan (SAP).

7.1 Sample Size

The primary objective of this trial is to show superiority of brexpiprazole (2 to 3 mg/day) + ADT over placebo + ADT in time to relapse of MDD signs and/or symptoms.

Time-to-relapse criteria are defined in the blinded addendum to this protocol. The 2-sided log-rank test will be used to test for statistical significance of the differences between the 2 survival curves.

Based on the results from a completed randomized withdrawal trial of olanzapine/fluoxetine combination versus fluoxetine monotherapy to assess prevention of relapse in subjects with treatment-resistant depression, it is reasonable to expect that 30% of subjects who receive placebo and 16% of subjects treated with brexpiprazole will relapse in 6 months, a hazard ratio of 0.49 (brexpiprazole + ADT versus placebo + ADT) is derived. Thus, 104 relapse events are needed in this trial to reach 95% power to test the primary hypothesis of the protocol at a 2-sided 0.05 alpha level. The sample size estimates used a 1:1 randomization ratio (brexpiprazole + ADT: placebo + ADT) which allowed 2 interim looks at 50% and 75% of events accrual time points. The O'Brian-Fleming boundaries were used for sample size calculation of the interim analysis so that the first interim analysis will be conducted when 52 relapse events are available and the second interim analysis will be conducted when 78 relapse events are available. The 2-sided alpha levels for these 2 interim analyses are 0.003 and 0.018 respectively, and the alpha left for the final analysis when 104 relapse events are available will be 0.044.

Protocol 331-201-00079

Assuming that each subject will be followed for 6 months after randomization and allowing for a 20% loss to follow-up, the projected total number of subjects to be randomized into the trial is 450. Using a 1:1 randomization ratio, the number of subjects to be randomized into each treatment group is 225. Assuming approximately 68% of subjects will progress from the Stabilization Phase (Phase B) to Double-blind Randomized Withdrawal (Phase C), it is expected that 700 subjects will be enrolled into the Stabilization Phase of the trial to allow 450 subjects to be randomized. Assuming approximately 55% subjects will progress from the Acute Treatment Phase to the Stabilization Phase, it is expected that approximately 1450 subjects will be enrolled into the Acute Treatment Phase. However, only the number of relapse events (ie, 104 events) is the hard sample size in this protocol. The other estimates, such as number of randomized subjects and number of subjects entering the Acute Treatment Phase and the Stabilization Phase, are only based on projection using assumptions that may or may not hold in this trial. Therefore, the actual number of subjects enrolled into the Acute Treatment Phase, the Stabilization Phase, or Double-blind Randomized Withdrawal Phase may vary from the projected values.

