	
Key Secondary Endpoints:
 
 • Change from randomization in the SDS mean total score at Week 46 (last observation carried forward) • Time-to-functional relapse based on SDS criteria 
Statistical Methods: The objective of the primary analysis is to compare the efficacy of brexpiprazole (2 to 3 mg/day) + ADT with that of placebo + ADT with regard to time-to-relapse. The statistical comparison will be performed by the log-rank test comparing the 2 treatment groups (brexpiprazole + ADT versus placebo + ADT) at an overall nominal significance level of 0.05 (2-sided) using the Double-blind Randomized Withdrawal (Phase C) Efficacy Sample.
 
Assuming that each subject will be followed for up to 26 weeks after randomization (Week 20) or until relapse, and allowing for a 20% loss to follow-up, the projected total number of subjects to be randomized into the trial (Phase C) is 450. Using a 1:1 randomization ratio, the number of subjects to be randomized into each treatment group is 225. Assuming approximately 68% of subjects will progress from Stabilization Phase to Double-blind Randomized Withdrawal Phase, it is expected that approximately 700 subjects will be enrolled into Stabilization Phase of the trial to allow 450 subjects to be randomized. Assuming approximately 55% subjects will progress from the Acute Treatment Phase to the Stabilization Phase, it is expected that approximately 1450 subjects will be enrolled into the Acute Treatment Phase. However, only the number of relapse events (ie, 104 events) is the hard sample size in this protocol. The other estimates, such as number of randomized subjects and number of subjects entering the Acute Treatment Phase and the Stabilization Phase, are only based on projections using assumptions that may or may not hold in this trial. Therefore, the actual number of subjects enrolled into the Acute Treatment Phase, the Stabilization Phase, or Double-blind Randomized Withdrawal Phase may vary from the projected values.
 
Trial Duration: The duration of this trial from first subject enrolled to last subject completed is estimated to be approximately 39 months, of which approximately 22 months are allotted for recruitment of subjects. Individual participation for subjects who complete the trial without early withdrawal will range from 47 to 55 weeks, consisting of a 3-day up to 6-week screening period, a 6- to 8-week single-blind Acute Treatment Phase, a 12-week single-blind Stabilization Phase, and up to 26-week

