7.3 Handling of Missing Data

For missing data resulting from early withdrawal from the trial in Phase C, subjects who withdraw early will be censored in the primary efficacy analysis at the time when they withdraw from the trial. In order to assess sensitivity of results due to missing data, two types of analyses will be performed for analyses by visit in Phases B and C: LOCF and OC. The LOCF and OC data sets are defined in the SAP. The OC data set will be used for analyses at each trial visit and the LOCF data set will be used for analyses at the last visit.

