Each subject will be followed for 26 weeks after randomization; allowing for a 20% loss to follow-up, the projected total number of subjects to be randomized into the trial is 450. Using a 1:1 randomization ratio, the number of subjects to be randomized into each treatment group is 225. Assuming approximately 68% of subjects will progress from the Stabilization Phase (Phase B) to Double-blind Randomized Withdrawal (Phase C), it is expected that 700 subjects will be enrolled into the Stabilization Phase of the trial to allow 450 subjects to be randomized. Assuming approximately 55% subjects will progress from the Acute Treatment Phase to the Stabilization Phase, it is expected that approximately 1450 subjects will be enrolled into the Acute Treatment Phase. However, only the number of relapse events (i.e., 104 events) is the determinate factor for sample size of this protocol. The other estimates, such as number of randomized subjects and number of subjects entering the Acute Treatment Phase and the Stabilization Phase, are only based on projection using assumptions that may or may not hold in this trial. Therefore, the actual number of subjects enrolled into the Acute Treatment Phase, the Stabilization Phase, or Double-blind Randomized Withdrawal Phase may vary from the projected values in order to reach the targeted 104 events.

5 Statistical Method

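### The projected 450 randomised subjects is the number needed with no loss to follow-up; the stated 20% allowance is not in it (about 500 to 510 would include it).

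*Protocol*

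**What the plan says.** Protocol section 7.1 assumes that "30% of subjects who receive placebo and 16% of subjects treated with brexpiprazole will relapse in 6 months". From this it takes a hazard ratio of 0.49 and 104 relapse events for 95% power at two-sided 0.05, with interim looks at 52 and 78 events. Each subject is followed for 6 months and, "allowing for a 20% loss to follow-up, the projected total number of subjects to be randomized into the trial is 450", that is, 225 per arm. The Synopsis (Statistical Methods) repeats this: "allowing for a 20% loss to follow-up, the projected total number of subjects to be randomized into the trial (Phase C) is 450". SAP section 4 carries the same figures.

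The Phase B projection is tied to the 450. With 68% progressing from Phase B to Phase C, "it is expected that 700 subjects will be enrolled into the Stabilization Phase of the trial to allow 450 subjects to be randomized". With 55% progressing from Phase A, about 1450 are to enter that phase.

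Protocol section 7.3 says how losses enter the primary analysis: "subjects who withdraw early will be censored in the primary efficacy analysis at the time when they withdraw from the trial".

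Both documents treat only the 104 events as fixed. SAP section 4 adds that the enrolled and randomised numbers "may vary from the projected values in order to reach the targeted 104 events".

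**The concern.** A projection that allows for loss should exceed the loss-free number. Here 450 matches the loss-free number almost exactly, so the text claims an allowance that the figure does not contain.

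Because follow-up in Phase C is capped at 26 weeks per subject, a shortfall in events cannot be recovered by following the same subjects for longer. It has to come from randomising more. A sponsor who plans sites, drug supply and timelines around 450 would therefore come up short of the final analysis even if every stated assumption held. If randomisation were closed at 450, the 95% power would not be reached.

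**Working it through.** **Inputs** (Protocol 7.1 and 7.4.4; SAP 4): 6-month relapse 30% on placebo and 16% on brexpiprazole; 1:1 allocation; 104 events; 6 months of follow-up; 20% loss; two-sided alphas 0.003051, 0.018325 and 0.044005 at 52, 78 and 104 events. Withdrawals are censored when they occur (Protocol 7.3).

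**Assumptions added here:** 30% and 16% are risks in the absence of loss; hazards are constant; loss is independent of relapse and equal in both arms. The documents do not give the loss pattern, so several are tried.

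**1. The event target reproduces.** HR = ln(0.84)/ln(0.70) = 0.489. With the stated boundaries, three-look power at 104 events is 95.0–95.1% for an HR of 0.489 to 0.49.

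**2. The 450 reproduces only without loss.** The mean risk is (0.30 + 0.16)/2 = 0.23.
- Events at 450: 450 × 0.23 = 103.5.
- N for 104 events: 104/0.23 = 452.

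**3. With 20% loss.** Over one 26-week period the relapse hazards are λ = −ln(0.70) = 0.357 on placebo and −ln(0.84) = 0.174 on brexpiprazole. With a constant loss rate γ, the probability of an observed event is λ/(λ+γ) × [1 − exp(−(λ+γ))]. For uniform loss times, 80% of subjects keep the full risk and 20% have the risk averaged over a uniform censoring time.

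| Loss pattern | P(event), placebo | P(event), brexpiprazole | Events at 450 | N for 104 events |
|---|---|---|---|---|
| Constant rate, γ = −ln(0.8) = 0.223 | 0.2707 | 0.1439 | 93.3 | 502 |
| Uniform over 26 weeks | 0.2718 | 0.1445 | 93.7 | 500 |
| 20% observed dropout, γ = 0.256 | 0.2666 | 0.1417 | 91.9 | 509 |

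For the first row: 225 × (0.2707 + 0.1439) = 93.3, and 208/(0.2707 + 0.1439) = 502.

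If lost subjects contributed no events at all, 450 would give 450 × 0.8 × 0.23 = 82.8 events, and 104 events would need 104/(0.23 × 0.8) = 565 subjects.

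**4. Power if randomisation stopped at 450.** Keeping looks at 52 and 78 events and placing the last look at the reduced count, with the stated alphas:
- 92 events: 92.3–92.5%
- 93 events: 92.6–92.7%
- 94 events: 92.8–93.0%

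**5. The enrolment chain.**
- Phase B: 700 × 0.68 = 476 randomised, giving 97.2–99.1 events with 20% loss, still short of 104.
- Phase A: 1450 × 0.55 × 0.68 = 542 randomised, giving 110.6–112.8 events, which is enough.
- For 500 to 510 randomised: 500/0.68 = 735 to 510/0.68 = 750 in Phase B, and 735/0.55 = 1337 to 750/0.55 = 1364 in Phase A.

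**The case against.** The strongest objection is about what 30% and 16% mean. The plan bases them on a completed withdrawal trial and does not say whether they are risks without loss or crude proportions already reduced by dropout. If crude, 450 would give 103.5 events with loss already counted. The hazard ratio does not settle this: solving for the hazards from crude 30% and 16% under constant-rate loss gives 0.485, which also rounds to 0.49. This reading cannot be excluded from the two percentages alone. But the plan states the relapse percentages first and then makes a separate 20% allowance when going from events to subjects. On the crude reading that allowance would have nothing left to do.

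Second, 500 to 510 depends on the loss pattern. That is true. Simple inflation gives about 565. In the other direction, the SAP counts events up to Day 196; running the hazards to that day with constant-rate loss gives about 474 to 482, with 97 to 99 events at 450. No pattern examined brings the number back to 450.

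A third possibility is a figure left over from another power level: 83 events for 90% power give 83/(0.23 × 0.8) = 451. The documents state 104 events and 95%, so this could explain the 450 but does not support it.

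Finally, the randomised number is openly a projection, only the events bind, and the stated 1450 in Phase A already implies enough subjects. This stands, and it limits the consequence. It does not correct the figure: the caveat covers assumptions that fail, whereas 450 falls short when all of them hold.

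**Conclusion.** The concern holds. The 450 is the loss-free number to within rounding (452), and the 20% allowance attributed to it is absent. With 20% loss, 450 subjects are expected to give about 92 to 94 events against 104. Reaching 104 takes about 500 to 510 randomised, some 50 to 60 more than projected.

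This rests on reading 30% and 16% as risks without loss, constant hazards, and non-informative loss spread over the 26 weeks. The size of the gap changes with the loss pattern; its direction did not change in any pattern tried.

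The error lies in the planning figure and in the 700 for Phase B. The 95% power belongs to the 104 events and is unaffected if randomisation continues to that count. It would fall to about 92–93% only if randomisation stopped at 450, which neither document provides for. The correction should be made because the stated number does not follow from its own assumptions in any of the three places where it is justified.

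**What to change.** In Protocol section 7.1, the Synopsis and SAP section 4, do one of the following:

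- **(a)** State that 450 assumes no loss to follow-up; that with 20% loss it would give about 93 events (about 92–93% power if randomisation stopped there); and that the number randomised will be raised as needed to reach 104.
- **(b)** Restate the projected number randomised as about 500 to 510 and the Phase B projection as about 735 to 750, naming the loss pattern assumed.

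Under either option, say whether the 30% and 16% are risks without loss, and keep 104 events as the binding target. Under (b), carry the new figures to the other places that repeat 450 and 700 (Synopsis, Trial Sites; Protocol 3.3.1; SAP 3.6).

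The cost is wording, plus either a larger stated projection or withdrawal of the 20% claim. The event target, boundaries, interim triggers, stated power and analysis do not change, and the 1450 for Phase A need not rise.

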Trial Sites:	It is anticipated that approximately 2100 subjects will be screened from approximately 75 sites to enroll approximately 1450 subjects into Phase A in order to enroll approximately 700 in Phase B and randomize 450 subjects in Phase C.
Investigational Medicinal Product(s), Dose, Dosage regimen, Treatment period, Formulation, Mode of Administration:	Treatment will consist of oral brexpiprazole plus 1 of 7 protocol-specified oral ADTs: citalopram hydrobromide (Celexa®), escitalopram (Lexapro®), fluoxetine (Prozac®), paroxetine (Paxil CR®) controlled-release tablets, sertraline (Zoloft®) tablets, duloxetine (Cymbalta®) delayed-release capsules, venlafaxine XR (Effexor XR®) extended-release (XR) capsules. Subjects will be on an adequate treatment as specified in the ATRQ. Brexpiprazole doses will be 2 to 3 mg/day depending on tolerability assessed during dose titration in Phase A. Doses of each ADT are listed in the protocol.
Trial Assessments:	
Efficacy: Montgomery Asberg Depression Rating Scale (MADRS), Clinical Global Impression - Severity of Illness Scale (CGI-S), and Sheehan Disability Scale (SDS)
 
Pharmacokinetic, Pharmacogenomics, [REDACTED] [REDACTED] plasma concentrations of brexpiprazole, cytochrome P450 (CYP) 2D6 metabolizer activity, [REDACTED] [REDACTED]
 
Safety: Adverse event (AE) reporting, clinical laboratory tests, 12-lead electrocardiogram, vital signs, physical examination, Simpson Angus Scale (SAS), Abnormal Involuntary Movement Scale (AIMS), Barnes Akathisia Rating Scale (BARS), and Columbia-Suicide Severity Rating Scale (C-SSRS)
 
Screening/Other: HAM-D17, Mini International Neuropsychiatric Interview (MINI), ATRQ, medical and medication history, psychiatric history, urine drug screening, urine pregnancy test

Criteria for Evaluation:	Primary Endpoint: The primary endpoint is time-to-relapse by any criteria as defined in the blinded addendum to this protocol.

Protocol 331-201-00079

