Stabilization Phase (Phase B): Subjects who meet response criteria at the end of the Acute Treatment Phase will continue to a 12-week Stabilization Phase (Phase B). The purpose of the Stabilization Phase is to ensure subjects are able to maintain stability of depression symptoms at the dose of brexpiprazole optimized during Phase A. To proceed to the Double-blind Randomized Withdrawal Phase (Phase C), subjects must meet the stability criteria as defined in the blinded addendum to the protocol. Subjects not meeting stability criteria will be discontinued from the trial.

Protocol 331-201-00079

Double-blind Randomized Withdrawal Phase (Phase C): Subjects eligible for the Double-blind Randomized Withdrawal Phase will be randomized 1:1 to double-blind treatment with brexpiprazole + ADT or placebo + ADT for up to 26 weeks. Transition from the Stabilization Phase to the Double-blind Randomized Withdrawal Phase should not be made evident to the subject. During the Double-blind Randomized Withdrawal Phase, subjects will be evaluated in the clinic at biweekly visits for the first 2 visits and monthly visits thereafter. Subjects meeting the criteria for relapse as defined in the blinded addendum to the protocol will be withdrawn due to lack of efficacy.

Follow-up: Subjects who are discontinued, withdrawn, or complete the trial will be followed up for safety 21 (+2) days after the last dose of investigational medicinal product (IMP) by telephone contact or clinic visit at the investigator's discretion. Subjects should be prescribed appropriate depression treatment as per the investigator or the subject's psychiatrist or primary care physician.

Protocol 331-201-00079

[figure not shown]

Figure 3.1-1 Trial Design Schematic

Protocol 331-201-00079

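### Does the projected Phase A enrolment of 1450 need correcting because it does not follow from the assumed 55% progression rate?

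*Protocol*

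**What the plan says.** Protocol 7.1 works backwards from the randomised phase. For the last step it assumes about 68% progression and concludes: "it is expected that 700 subjects will be enrolled into the Stabilization Phase of the trial to allow 450 subjects to be randomized". The sentence after that gives the Phase A projection: "Assuming approximately 55% subjects will progress from the Acute Treatment Phase to the Stabilization Phase, it is expected that approximately 1450 subjects". Both the Synopsis (Statistical Methods) and SAP section 4 give the same rates and counts. The Synopsis (Trial Sites), Protocol 3.3.1 and SAP 3.6 repeat 1450, 700 and 450 without the rates.

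The same paragraph of Protocol 7.1 then limits what these counts mean. Only the 104 relapse events are fixed, and the numbers randomised or entering Phases A and B "are only based on projection using assumptions that may or may not hold in this trial". SAP section 4 says that the event count "is the determinate factor for sample size of this protocol" and that enrolment in each phase may move away from the projections in order to reach 104 events.

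**The concern.** The sentence presents 1450 as the consequence of a 55% progression rate and a Phase B target of 700, and a reader who does the division gets a different number. The word approximately does not close a gap of this size. The caveat that assumptions may fail concerns observed rates that differ from planned ones. It does not explain a projection that departs from its own stated assumption.

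The Phase A count is also not idle. It is the number of people expected to receive single-blind brexpiprazole before any randomisation, and the Synopsis lists it beside the screening and site numbers: "approximately 2100 subjects will be screened from approximately 75 sites to enroll approximately 1450 subjects into Phase A". If 1450 were an error in a quantity that drove power or the stopping of enrolment, the trial could be mis-sized. If the true planning rate were 48% rather than 55%, the text would give an optimistic picture of how many subjects respond and continue.

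**Working it through.** **Inputs.** From Protocol 7.1, with the same values in the Synopsis and SAP section 4: progression A to B 55%; progression B to C 68%; Phase A 1450; Phase B 700; randomised 450; events 104.

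**Reproducing the stated Phase A count.** Phase A needed = Phase B / rate.

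- 700 / 0.55 = 1272.7, so 1273. Stated: 1450. Difference 1450 − 1273 = 177; ratio 1450 / 1272.7 = 1.139.
- Forward: 1450 × 0.55 = 797.5, so 798. Stated: 700.
- Implied rate: 700 / 1450 = 48.3%. Stated: 55%.

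The stated figure is not reproduced.

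**Could rounding explain it?**

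| Rate A to B | Phase A needed for 700 |
|---|---|
| 55.5% | 1261 |
| 54.5% | 1284 |
| 52.5% | 1333 |
| 50% | 1400 |
| 48% | 1458 |

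Only a rate near 48% gives 1450.

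**Other routes tried.** Chaining both rates from 450 gives 450 / 0.68 / 0.55 = 1203. Applying the 20% loss to follow-up to Phase A, where the text does not put it, gives 1273 / 0.8 = 1591 or 1273 × 1.2 = 1527. None gives 1450.

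**Could further attrition explain it?** Protocol 3.1 says "Subjects who meet response criteria at the end of the Acute Treatment Phase will continue to a 12-week Stabilization Phase (Phase B"), but response is not the only gate. Table 3.4.3-1 also applies criteria 35 (illicit drug result) and 36 (safety concern) at Weeks 6 to 8. SAP 3.3 lists completing Phase A and meeting response criteria as separate items. If 55% were a response rate, the remaining factor needed is 0.483 / 0.55 = 0.878, a further loss of about 12%. That is an assumption. The documents do not say it, and they word the 55% as the rate of progression itself.

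**The adjacent step.** 450 / 0.68 = 661.8, so 662, against 700 stated (38 more, 5.8%). Forward, 700 × 0.68 = 476 against 450. The gap has the same direction and is smaller.

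**Direction and consequence.**

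- Stated rates applied to 1450: 1450 × 0.55 × 0.68 = 542 randomised, which is 92 above 450.
- Lower A to B rate implied by the counts, with the stated 68%: 1450 × 0.483 = 700, then 700 × 0.68 = 476, still above 450.
- Combined rate at which 1450 just yields 450: 450 / 1450 = 31.0%, against 0.55 × 0.68 = 37.4% assumed.

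Whichever of the three figures is out of line, 1450 in Phase A supplies at least 450 randomised subjects under the stated 68%.

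**Does the 104-event target depend on it?** Protocol 7.1 derives 104 events from a hazard ratio of 0.49, 95% power, two-sided alpha 0.05, 1:1 allocation and two interim looks. No Phase A or Phase B count enters that calculation.

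**The case for a change.** The best case for a correction is that the inconsistency is verifiable, appears in three places and would cost one clause in each to repair. A reader cannot tell whether the sponsor expects 48% or 55% to progress, or whether a deliberate margin of about 177 was built in. The possible explanations are all unstated: a margin is not declared, a later attrition step is not described as such, and the 20% loss to follow-up is attached to the randomised subjects.

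Most of that stands as description. The three figures do not agree, the documents do not show which is out of line, and the caveat about assumptions does not explain it. What does not stand is the step from there to a needed change. The proposed repair would disclose a margin or restate a planning rate and leave every count as it is. It would not alter who is enrolled, when the trial stops, or how anything is tested. Nor can effects on screening or site numbers be claimed: the Synopsis lists 2100 screened and 75 sites beside the 1450 but derives neither from it.

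**Conclusion.** The arithmetic criticism is right, but it does not call for a change. The 55%, 700 and 1450 are mutually inconsistent by 177 subjects in Phase A (13.9%), or 48.3% against 55% as a rate. The 68% step has a 5.8% surplus of the same kind, and the same reasoning applies to it.

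The discrepancy lies in a projection that both documents declare non-binding. The trial runs to 104 events, and enrolment may vary to reach them. The error is towards over-provision, so it does not threaten the planned 450 randomised. The event target, power, interim and final alpha levels, and all analyses are the same whichever figure is out of line.

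This conclusion rests on two things: that 104 events remains the governing size, as both documents state, and that the 1450 is treated as a forecast rather than a quota, as the wording in Protocol 7.1 and SAP section 4 allows. On that footing, the mismatch is a clerical looseness or an undeclared cushion in a recruitment forecast, and following the plan as written still gives sound results.
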